7.4.1.4.2 Expedited Adverse Event Reporting

Expedited AE reporting for this study must use the reporting procedures briefly outlined in the table below.

Expedited Reporting Guidelines – Reporting Requirements for Adverse Events that occur within 30 Days¹ of the Last dose of the Investigational Agent on Phase 2 and 3 Trials

	Grade 1	Grade 2	Grade 2	Grade 3		Grade 3	Grades 4 & 5 ²		Grades 4 & 5 ²
	Un- expected and Expected	Un- expected	Expected	Unexpected		Expected	Unexpected		Expected
				with Hospitalization	without Hospitalization		with Hospitalization	Without Hospitalization	
Unrelated Unlikely	Not Required	Not Required	Not Required	10 Calendar Days	Not Required	10 Calendar Days	Not Required	10 Calendar Days	10 Calendar Days
Possible Probable Definite	Not Required	10 Calendar Days	Not Required	10 Calendar Days	10 Calendar Days	10 Calendar Days	Not Required	24-Hour; 5 Calendar Days	10 Calendar Days

¹ Adverse events with attribution of possible, probable, or definite that occur greater than 30 days after the last dose of treatment require reporting as follows:

24-hour notification followed by complete report within 5 calendar days for:

- Grade 4 and Grade 5 unexpected events

10 calendar day report:

- Grade 3 unexpected events with hospitalization or prolongation of hospitalization
- Grade 5 expected events

² Although a 24-hour notification is not required for death clearly related to progressive disease, a full report is required as outlined in the table.

Note: All deaths on study require both routine and expedited reporting regardless of causality. Attribution to treatment or other cause must be provided.

- Expedited AE reporting timelines defined:
- "24 hours; 5 calendar days" – The investigator must initially report the AE within 24 hours of learning of the event followed by a complete report within 5 calendar days of the initial 24-hour report.

- "10 calendar days" - A complete report on the AE must be submitted within 10 calendar days of the investigator learning of the event.
- Any medical event equivalent to CTCAE grade 3, 4, or 5 that precipitates hospitalization (or prolongation of existing hospitalization) must be reported regardless of attribution and designation as expected or unexpected with the exception of any events identified as protocol-specific expedited adverse event reporting exclusions.
- Any event that results in persistent or significant disabilities/incapacities, congenital anomalies, or birth defects must be reported.

7.4.1.5 Expected adverse events

For this study, the applicable reference document is the most current version of the investigator's brochure (IB) / summary of product characteristics.

Overview listings of frequent events that have occurred so far in the clinical development are shown in the current IB. If relevant new safety information is identified, the information will be integrated into an update of the IB and distributed to all participating sites.

The expectedness of AEs will be determined by Bayer according to the applicable reference document and according to all local regulations.

7.4.1.6 Adverse events of special safety interest

As with any new chemical entity, there is always potential for unexpected adverse events, including hypersensitivity reactions.

Based on data studies with Regorafenib and from current knowledge of the pharmacological properties of other small molecule tyrosine kinase inhibitors in this drug class, as soon as there is reasonable suspicion of any of the following AEs, the investigator should immediately notify the sponsor as outlined in Section 7.4.1.4.

Reportable adverse events include:

- Acute renal failure (NCI-CTCAE version 4.0 \geq grade 3) or severe proteinuria (NCI-CTCAE version 4.0 \geq grade 3)
- Interstitial lung disease
- Acute cardiac failure
- Clinically significant bleeding (NCI-CTCAE version 4.0 \geq grade 3)
- Stevens-Johnson Syndrome and erythema multiforme
- Hepatic failure
- Reversible posterior leukoencephalopathy syndrome
- Gastrointestinal perforation or fistula

7.4.2 Pregnancies

The investigator must report to Bayer any pregnancy occurring in a study subject, or in his partner, during the subject's participation in this study. The report should be submitted within the same timelines as an SAE, although a pregnancy per se is not considered an SAE.

For a study subject, the outcome of the pregnancy should be followed up carefully, and any abnormal outcome of the mother or the child should be reported.

For the pregnancy of a study subject's partner, all efforts should be made to obtain similar information on course and outcome, subject to the partner's consent.

For all reports, the forms provided are to be used.

7.4.3 Further safety

Progressive disease

If progressive disease leads to signs and symptoms that meet the criteria for an SAE (i.e., hospitalization, disability, death, or important medical event), the signs and symptoms should be reported as an SAE and not the underlying progressive disease.

Death

If any subject dies during the trial or within 30 days of the end-of-treatment visit, the investigator will inform Bayer and record the cause of death in detail (using the SAE Form) within 24 hours.

7.5 Appropriateness of procedures / measurements

The assessments described in the previous sections are widely used and generally recognized as reliable, accurate, and relevant for determining the safety and efficacy of therapies in this disease.

8. Statistical methods and determination of sample size

8.1 Analysis sets

This is a one-stage, non-randomized, phase II trial conducted at UAB Comprehensive Cancer Center, Wayne State University and Progression-free survival at 6 months (PFS6) is chosen as the primary end-point. A total of 35 patients will be enrolled for this trial. Accrual period will be 6 to 12 months.

8.2 Variables

All patients will be screened before enrollment and demographic information about age, gender, race, height and smoking status will be collected. Weight, blood pressure measurements, and tumor measurements using CT scans will be noted at baseline visits and subsequent clinic visits.

All patients will be evaluable for toxicity from the time of their first treatment with Regorafenib. CTCAE v 4.03 will be utilized to grade toxicities (Section 13.5). All evaluable patients included in the study will be assessed for response to treatment, even if there are major protocol treatment deviations. Each patient will be assigned one of the following categories: 1) complete response, 2) partial response, 3) stable disease, 4) progressive disease, 5) early death from malignant disease, 6) early death from toxicity, 7) early death because of other cause, or 9) unknown (not assessable, insufficient data). [Note: By arbitrary convention, category 9 usually designates the "unknown" status of any type of data in a clinical database.]

All of the patients who met the eligibility criteria (with the possible exception of those who received no study medication) will be included in the main analysis of the response rate. Patients in response categories 4-9 will be considered to have a treatment failure (disease progression). Thus, an incorrect treatment schedule or drug administration will not result in exclusion from the analysis of the response rate. Precise definitions for categories 4-9 will be protocol specific.

All conclusions will be based on all eligible patients. Sub-analyses may then be performed on the basis of a subset of patients, excluding those for whom major protocol deviations have been identified (e.g., early death due to other reasons, early discontinuation of treatment, major protocol violations, etc.). However, these sub-analyses will not serve as the basis for drawing conclusions concerning treatment efficacy, and the reasons for excluding patients from the analysis will be clearly reported. The 95% confidence intervals will also be provided.

8.3 Statistical and analytical plans

The primary endpoint of the study is the rate of progression free survival (PFS) at 6 months (PFS6). Given the poor prognosis of this patient population and data from other studies of salvage therapy, a PFS6 of $\geq 20\%$ is felt to be important for this regimen, while a PFS6 $< 5\%$ is felt to be of poor interest. The trial also enrolls patients who progress within 6 months of last cycle of prior chemotherapy to enhance the interpretability of outcomes, since such patients are unlikely biologically to be progression-free for 6 more months without active therapy that favorably impacts on tumor biology to extend PFS. SAS version 9.3 was used to calculate power. The justification for the proposed sample size is based on an exact test for a binomial proportion with a one-sided significance level of 5%. With 32 evaluable subjects,

we will have approximately 80% power (79.6%) to reject the null hypothesis that PFS6 is < 5% in favor of PFS6 \geq 20%. Given that 5-10% of patients may be inevaluable, up to 35 patients may be enrolled. If five or more patients remain progression-free at 6 months, this regimen will be considered to be of significant interest.

Chi-square or Fisher's exact test will be employed to determine univariate association of biomarker status with PFS6 and objective response. Descriptive statistics including frequencies and proportions will be calculated to summarize safety and toxicity outcomes. Specifically, the number of adverse events (AE) and serious adverse events (SAE) will be tabulated and summarized. Point estimates and exact binomial (Clopper-Pearson) confidence intervals (CI) will be calculated to estimate the incidence of AEs and SAEs. The precision of these estimates, i.e., width of the confidence interval, will depend on the estimated incidence of each outcome. The table below gives the exact 95% confidence intervals for a range of incidences, assuming 32 evaluable subjects.

Number of subjects experiencing event	Estimated Incidence	95% Exact CI for Incidence		Width of CI
		Lower Limit	Upper Limit	
1	0.031	0.001	0.162	0.161
2	0.062	0.008	0.208	0.200
4	0.125	0.035	0.290	0.255
8	0.250	0.115	0.434	0.319
16	0.500	0.319	0.681	0.362

A secondary objective is comparison of observed PFS6 vs. predicted PFS6 based on previously published nomogram. (17, 66). This internally and externally validated and calibrated nomogram uses PS (performance status), LM (liver metastasis), Hb (hemoglobin) and TFPC (time from prior chemotherapy) to predict PFS6 for an individual subject receiving historically used agents such as taxanes. We will use this nomogram to predict PFS6 for the patients in our study and compare the predicted values to the observed PFS6. The concordance index (c) will be calculated as a measure of the nomogram's discrimination ability. Predicted PFS will also be plotted against the observed PFS6 to provide a visual comparison.

9. Data handling and quality assurance

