Diagnosis and main criteria for inclusion	Pathologically or cytologically confirmed locally advanced unresectable or metastatic invasive transitional cell carcinoma of the urothelium Progressive disease following 1-3 chemotherapy regimens	
Study design	Metastatic UC progressing after prior chemotherapy (N=35) → (15 slides of 10 µM sections, slides of 5 µM sections) 
 
  Regorafenib 120 mg po for 21 days of 28 days in cycle 1 increased to 160 mg po daily from cycle 2 or later if no Regorafenib- 
 
 Archival FFPE slides  Clinical and laboratory daily evaluation day 1 of each 28 day cycle  Radiologic evaluation every 8 weeks 
 
 
 
  Continue therapy until disease progression or intolerable toxicities 
 
  
 
	

Type of control	No control arm in this nonrandomized study
Number of subjects	35 patients; 4 sites
Plan for statistical analysis	A minimum of 32 evaluable subjects will be included in final analysis. Given that 5-10% of patients may be inevaluable, up to 35 patients may be enrolled. The alpha level of the design is 0.05 and the power is 0.8. Chi-square or Fisher's exact test will be employed to determine univariate association of biomarker status with PFS6 and objective response.

Table of contents

Title page.....	1
Synopsis.....	4
Table of contents	6
List of abbreviations.....	8
1. Introduction.....	10
1.1 Background.....	10
1.2 Rationale of the study	15
1.3 Regorafenib.....	16
1.3.1 Preclinical.....	16
1.3.2 Clinical experience.....	17
2. Study objectives.....	18
3. Investigator[s] and other study participants.....	18
4. Study design.....	19
5. Study population	19
5.1 Eligibility.....	19
5.1.1 Inclusion criteria.....	19
5.1.2 Exclusion criteria	20
5.1.3 Excluded therapies and medications, previous and concomitant.....	22
5.1.4 Selection of study population.....	22
5.2 Withdrawal of subjects from study	23
5.2.1 Withdrawal.....	23
5.2.2 Screen Failures/Dropouts	24
5.2.3 Replacement	24
6. Treatment[s].....	24
6.1 Treatments to be administered	24
6.2 Treatment assignment.....	24
6.2.1 Regorafenib.....	24
6.3 Blinding.....	24
6.3.1 Study Treatment.....	25
6.3.1.1 Dose Reduction Levels.....	25
6.3.1.2 Hypertension	29

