Historical pooled PFS6 is approximately 20% for previously used agents. In this study, those progressing within 6 months of prior therapy will be enrolled with the goal of detecting PFS6 in $\geq 20\%$ of patients, while PFS6 in <5% will be considered to be of poor interest. Selecting patients following 1-3 prior regimens and within 6 months of prior therapy will ensure timely accrual of a homogeneous population and enrich for patients unlikely to attain PFS6 without active therapy. Thus, outcome results will be more interpretable, given these stipulations. Tumor tissue will be collected to be studied retrospectively to analyze genomics/proteomics to identify an association with PFS6.

Nanostring platform for gene expression analysis of formalin-fixed paraffin embedded tumor

Gene expressing profiling performed by the nanostring technology, which utilizes formalin-fixed paraffin embedded (FFPE) tissue using the nCounter® appears highly promising (59). This technology provides robust data from FFPE tissue using the nCounter® GX Kit and offers high levels of precision and sensitivity (>1 copy per cell) without the need for amplification of ≥ 100 ng of RNA. Nanostring is a multiplexed (up to 800 genes per reaction) platform, which utilizes digital counting and excellent quantitative reproducibility by employing two ~50 base probes per mRNA that hybridize in solution. Multiple successful applications utilizing the nCounter System to subtype tumors, formulate tumor prognostic signatures, or discover novel targets for therapy have been reported in other malignancies (60-63). Notably, the 50-gene PAM50 signature (Prosigna™) derived from nanostring was approved by the US FDA in 2013 to assess the risk of distant recurrence at 10 years in postmenopausal women with hormone receptor-positive breast cancer. Indeed, the PAM50 gene score, which is enriched for proliferation-associated genes appeared more robust than the Oncotype DX® recurrence score in predicting recurrence (62). Gene expression by nanostring may be proposed for a highly relevant panel of 797 genes including 230 human cancer-promoting genes, 519 kinase genes, 32 bladder cancer specific genes recently reported by TCGA including 4 genes involved in epigenetic regulation, 85 DNA damage repair genes, 3 stem cell relevant genes and 8 internal reference genes (64).

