7.2.2 Exploratory tumor tissue studies and central pathology review

Twenty archival formalin-fixed paraffin-embedded (FFPE) tumor slides will be requested for potential central pathology review and molecular studies. Fifteen slides of 10 μM thickness sections each and 5 slides of 5 μM thickness sections each will be requested from all institutions. In the event of attainment of the primary endpoint (i.e. PFS6 in $\geq 20\%$ of patients), slides will be obtained and following central pathology review for determining histologic subtype, tumor will be demarcated from adjacent normal tissue on the H+E slide to guide procurement of tumor-enriched samples. The 10 μM sections will be used for RNA isolation toward gene expression profiling for ~ 800 cancer-promoting, kinase, DNA-damage repair, bladder cancer-specific and stem cell panel genes by the nanostring platform performed centrally in the UAB Comprehensive Cancer Center. A total surface area of tumor 100 mm^2 is adequate to harvest the necessary amount of RNA (100 ng) using the RNAeasy Mini Kit (Qiagen), and the quality of the RNA will be assessed via the 260/280 ratio using nanodrop. [name] at UAB Radiation Oncology Dept. will perform the nanostring studies as described in previous publications utilizing the nCounter by inputting RNA directly into a hybridization reaction containing color-coded molecular barcodes representing the genes of interest [56]. Immunohistochemistry (IHC) is performed on the 5 μM section slides for VEGFR2 and Tie2 by previously described methods using appropriate controls.

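### Sections 8.3 and 7.2.2 set different bars for a positive primary result: five progression-free patients (15.6% of 32) against an observed PFS6 of at least 20% (seven patients)

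*Combined protocol and SAP*

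**What the plan says.** Section 8.3 sizes the trial with an exact one-sided 5% binomial test on the PFS6 rate. With 32 evaluable patients, "we will have approximately 80% power (79.6%) to reject the null hypothesis that PFS6 is < 5% in favor of PFS6" of at least 20%. Up to 35 patients may be enrolled to allow for inevaluable ones, and the synopsis states: "A minimum of 32 evaluable subjects will be included in final analysis". Section 8.3 then gives its only decision rule: "If five or more patients remain progression-free at 6 months, this regimen will be considered to be of significant interest".

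Section 7.2.2 makes the tissue work depend on the primary result and defines that result in a parenthesis: "In the event of attainment of the primary endpoint (i.e. PFS6 in $\geq 20\%$ of patients), slides will be obtained".

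The 20% figure also appears in Section 1.2, as the design aim: "with the goal of detecting PFS6 in $\geq 20\%$ of patients". Section 8.3 plans the biomarker analyses with no condition on the primary result: "Chi-square or Fisher's exact test will be employed to determine univariate association of biomarker status with PFS6 and objective response".

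**The concern.** In Sections 1.2 and 8.3, 20% is a true rate: the level of activity the trial is meant to detect and at which power is calculated. In 7.2.2 the same figure is applied to the trial's result, as the bar that the data must reach. These are different things. A test of 5% against 20% rejects at an observed rate well below 20%, and here it does so at five patients.

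With five or six progression-free patients the two sections disagree. Under 8.3 the result is positive. Under 7.2.2 the primary endpoint is not met and the condition for obtaining slides fails, so the association tests planned in 8.3 would have no tissue data if 7.2.2 were followed. The report would also have support in the plan for two opposite statements about the primary endpoint, and the choice between them would be made after the data were seen.

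**Working it through.** **Inputs (Section 8.3):** null rate 5%, alternative 20%, exact binomial test at one-sided 5%, n = 32 evaluable, up to 35 enrolled, cut-off of five. **From Section 7.2.2:** PFS6 of at least 20%.

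**Formula.** For X ~ Binomial(n, p), a rule of at least r successes has alpha = P(X ≥ r | p = 0.05) and power = P(X ≥ r | p = 0.20).

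**Step 1: reproduce the plan's figure (n = 32).**
- r = 4: alpha 0.0738, above 5%, so not allowed.
- r = 5: alpha 0.0204, power 0.7956. This is the stated 79.6%.

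Five is the smallest valid cut-off. The sample size, test, cut-off and power in 8.3 agree with each other.

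**Step 2: turn the 20% bar into a count.** 0.20 × 32 = 6.4 and 0.20 × 35 = 7.0, so seven patients are needed at every n from 32 to 35.

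**Step 3: compare the rules.** The last column is P(X ≥ 5) − P(X ≥ 7) at a true 20%, taken from unrounded values.

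| n | 5/n | 6/n | 7/n | Alpha, ≥5 | Power, ≥5 | Power, ≥7 | P(5 or 6) at 20% |
|---|---|---|---|---|---|---|---|
| 32 | 15.6% | 18.8% | 21.9% | 0.0204 | 0.7956 | 0.4645 | 0.3311 |
| 33 | 15.2% | 18.2% | 21.2% | 0.0230 | 0.8179 | 0.4996 | 0.3183 |
| 34 | 14.7% | 17.6% | 20.6% | 0.0259 | 0.8381 | 0.5339 | 0.3043 |
| 35 | 14.3% | 17.1% | 20.0% | 0.0290 | 0.8565 | 0.5672 | 0.2893 |

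At n = 32 and a true 20%, the share of results that pass 8.3 but fail 7.2.2 is 0.3311 / 0.7956 = 0.416, about 42%.

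**Step 4: vary the true rate (n = 32).**

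| True PFS6 | 5% | 10% | 15% | 20% | 25% | 30% |
|---|---|---|---|---|---|---|
| P(5 or 6) | 0.0195 | 0.1756 | 0.3409 | 0.3311 | 0.2081 | 0.0942 |

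The maximum is 0.3590, at a true rate of 17.1%.

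**Step 5: could a larger trial rescue an observed 20% bar?** No. When the bar equals the true rate, the chance of reaching it stays near one half. With n = 100, P(X ≥ 20 | p = 0.20) = 0.5398.

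**The case against.** The strongest reply is that 7.2.2 does not state a rival rule. Section 8.3 describes its test as rejecting in favour of a PFS6 of at least 20%, so the parenthesis in 7.2.2 may be shorthand for rejecting the null. It gives no count and does not say that the rate is an observed one. Section 8.3 in turn never says that the primary endpoint is met; it says only that the regimen is of interest. A report writer would take the efficacy conclusion from the statistical section.

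The tissue consequence can also be softened. The schedule in Section 7.1 requests the slides at screening, Section 1.2 says that tissue will be collected for retrospective study, and Section 7.2.1 makes the immunohistochemistry and gene-expression work optional and dependent on outcomes. Slides may therefore already be in hand, and omitting the laboratory work would break no firm commitment.

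The second part largely stands. Loss of the tissue data follows from 7.2.2 as written, but it is not certain in practice, and the work is exploratory. The first part does not stand. The sentence in 7.2.2 is a trigger that acts on the trial's result, and a true rate is never observed, so it can only be applied to the observed proportion. It also defines explicitly what meeting the primary endpoint means. Five of 32 rejects a rate of 5%; it does not show a rate of 20%.

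**Conclusion.** The inconsistency is real and should be fixed. With five or six progression-free patients (14.3% to 18.8%, depending on the denominator), 8.3 and 7.2.2 give opposite answers on the primary result, and nothing in the documents reconciles them. At a true PFS6 of 20% the probability of landing there is 29% to 33% for 35 down to 32 analysed patients. With 32 patients it lies between 17.6% and 35.9% for true rates from 10% to 20%.

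These figures assume independent binary outcomes and between 32 and 35 analysed patients. The count of seven is the same across that range, so the conflict does not depend on which denominator is used. The 8.3 rule itself is correct, and its alpha, power and sample size are untouched. The likely source is that the design alternative was carried into 7.2.2 as an observed cut-off. The direct operational effect is limited to the exploratory tissue work; the wider risk is a report with two readings of its primary endpoint.

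**What to change.** In Section 7.2.2, replace the parenthesis with: *(i.e. five or more patients progression-free at 6 months, per Section 8.3)*. Optionally, add to Section 8.3 that 20% is the true rate at which power is evaluated and not a bar for the observed rate. While editing, it would help to say whether the count is taken over evaluable patients (8.3) or all eligible patients (8.2), and whether 7.2.2 restricts collection of the slides or only the laboratory work, since Section 7.1 requests them at screening.

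The cost is one parenthesis and an optional clause. Sample size, test, alpha and power do not change; the five-patient rule keeps exact alpha between 0.020 and 0.029 for 32 to 35 patients.

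If the sponsor really intends an observed 20% bar, Section 8.3 must change instead: the count becomes seven and the stated power falls to about 46% (7 of 32) or 57% (7 of 35). Enrolling more patients would not restore 80%. Whichever rule is kept, it should be fixed before the primary result is analysed.

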2.3 Exploratory objectives

- Association of tumor IHC for Tie2 and VEGFR2 with PFS
- Association of Gene expression in tumor tissue using Nanostring technology

3. Investigator[s] and other study participants

Principal Investigator

[name]
UAB Comprehensive Cancer Center
[name]
[name]
[contact]
[contact]
Email address: [contact]

Co-Investigators

[name]
[name]
[name]

[name], MD is a Professor in Department of Medicine, division of Hematology and Oncology at University of Alabama at Birmingham (UAB) and a Scientist at UAB Comprehensive Cancer Center (UABCCC). [name] is the director of urologic oncology at Wayne State University Karmanos Cancer Institute, and has extensively accrued in urothelial cancer trials and published multiple studies. [name], MD is an

[figure not shown]
Assistant Professor in the Department of Medicine, Division of Hematology and Oncology at UAB. He will see patients at Kirklin clinic along with [name]. [name] is a faculty urologic medical oncology physician with Cleveland Clinic where he is active with clinical trials and patient care.

4. Study design

This is a 3-center one-stage phase II trial conducted at the UAB Comprehensive Cancer Center (Birmingham, AL), Wayne State Karmanos Cancer Institute (Detroit, MI), and the Cleveland Clinic (Cleveland, OH). The trial will be managed by the Clinical Trial Network Monitoring Office (CTNMO) housed at the UAB Comprehensive Cancer Center. Progression free survival at 6 months is the primary end- point and the trial will enroll 35 patients. The eligible population includes patients with advanced urothelial cell carcinoma who have progressive disease after 1-3 prior chemotherapy regimens. Regorafenib is taken orally and is administered daily for the first 21 days of each 28 day cycle. The dose of Regorafenib is 120 mg once daily for the first cycle, which will be escalated to 160 mg once daily from the second cycle if no Regorafenib-related toxicities greater than grade 1 occur. Each 28 day cycle will be repeated until disease progression, intolerable toxicities, or patient decision with no limit on number of cycles allowed. Radiological evaluations are performed at each institution using RECIST 1.1 criteria every 2 cycles (8 weeks) or earlier if clinically indicated. Progression free-survival will be defined as the time to first occurrence of any of the following:

1. Clinical symptoms and signs of progression of disease,

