7.2 Efficacy

7.2.1 End points of efficacy

The primary endpoint of the study is to evaluate progression free survival (PFS) at 6 months (PFS6). Secondary endpoints of this study are evaluating measurable disease response rate using RECIST 1.1 criteria, measuring survival and toxicities after receiving Regorafenib.

Immunohistochemistry and gene expression using Nanostring technology for a panel of kinase and cancer associated genes to correlate with tumor response may be performed and are potential endpoints based on outcomes.

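### The only biomarker tests named are categorical tests of an undefined biomarker status, although Nanostring expression is a quantitative count and no cut-point or full-scale method is given

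*Combined protocol and SAP*

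**What the plan says.** Section 8.3 and the statistical paragraph of the synopsis contain the whole biomarker analysis: "Chi-square or Fisher's exact test will be employed to determine univariate association of biomarker status with PFS6 and objective response".

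The markers are set out elsewhere.

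- Section 2.3 lists two exploratory objectives: "Association of tumor IHC for Tie2 and VEGFR2 with PFS" and "Association of Gene expression in tumor tissue using Nanostring technology". The second names no outcome.
- Section 1.2 describes a platform that "utilizes digital counting and excellent quantitative reproducibility", and proposes a "highly relevant panel of 797 genes".
- Section 7.2.2 plans "gene expression profiling for ~ 800 cancer-promoting, kinase, DNA-damage repair, bladder cancer-specific and stem cell panel genes by the nanostring platform", plus IHC for VEGFR2 and Tie2 on the thinner sections.
- Section 7.2.1 says of this work that it "may be performed and are potential endpoints based on outcomes". Section 7.2.2 makes obtaining the slides conditional on attaining the primary endpoint.

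No section defines biomarker status, gives an IHC scoring scale or a cut-point, names a test for a marker kept on a numerical scale, or says how several hundred tests will be handled together.

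**The concern.** The assay yields a count for each gene, but the tests named accept only categories. To follow Section 8.3, the analyst must first turn each count into groups by a rule that the plan does not state. If no rule is fixed beforehand, it would be chosen once outcomes are known, because tissue work starts only after the primary endpoint has been met.

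Few successes are available. Section 8.3 calls five or more of 32 a success. The 20% trigger in Section 7.2.2 means 0.20 × 32 = 6.4, so at least 7. With 5 to 7 patients in the smaller group, categorising the marker gives up power that the same data could supply. A discrete exact test also puts a floor under the p-value, however cleanly a gene separates the groups. What is at stake is the exploratory objective only.

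**Working it through.** **The plan's own figure.** The documents give no power for a biomarker test. The one power figure in Section 8.3 does reproduce: with n = 32, a null rate of 5%, an alternative of 20% and success at 5 or more, P(X ≥ 5 | 32, 0.20) = 0.7956, against the stated 79.6%. The actual one-sided size is P(X ≥ 5 | 32, 0.05) = 0.0204. So 32 patients and 5 successes are sound starting inputs.

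**Inputs taken from the plan:** 32 evaluable patients; 5 to 7 successes, as derived above; 797 genes (Section 1.2).

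**Assumptions not in the plan:** normal log-expression with equal variances; a shift d, in SD units, between successes and failures; a median split (16 high, 16 low); a two-sided 5% level.

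**Step 1. When the median-split Fisher test can be significant.** With k successes, the most extreme table puts all k on one side of the median. Its two-sided p-value is 2·C(16,k)/C(32,k):

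- k = 5: 2 × 4,368 / 201,376 = 0.043
- k = 6: 2 × 8,008 / 906,192 = 0.018
- k = 7: 2 × 11,440 / 3,365,856 = 0.0068

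For k = 7, the next table (6 against 1) has p = 2 × (11,440 + 8,008 × 16) / 3,365,856 = 0.083, which is not significant. For k = 5 and 6 the next table is not significant either. The test therefore rejects only if every success falls on the same side, and the p-values listed are also its actual sizes.

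**Step 2. Power by simulation** (20,000 runs per cell).

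| Successes of 32 | d | Wilcoxon | Fisher, median split | Loss (points) |
|---|---|---|---|---|
| 5 | 1.0 | 46.6% | 32.6% | 14 |
| 5 | 1.2 | 60.6% | 43.1% | 18 |
| 6 | 1.0 | 53.4% | 23.2% | 30 |
| 6 | 1.2 | 69.3% | 33.5% | 36 |
| 7 | 1.0 | 58.6% | 16.5% | 42 |
| 7 | 1.2 | 74.1% | 25.7% | 48 |

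A separate run of 4,000 replicates gave 25.9% against 74.7% in the last row, a loss of 49 points. The range is therefore about 14 to 49.

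**Step 3. Separating the split from Fisher's conservatism.** Wilcoxon was run at Fisher's own actual size, with d = 1.2. It gave 59% against 43% (5 successes), 49% against 33% (6) and 41% against 26% (7). The split alone therefore costs about 16, 16 and 15 points. Taking these from the totals of 18, 36 and 48 leaves about 2, 20 and 33 points for Fisher's discreteness.

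**Step 4. Uncorrected chi-square on the same split.** At 5 and 6 successes it rejects for the same tables as Fisher, so its power is the same. At 7 successes it also rejects the 6-against-1 table: χ² = 32 × (6 × 15 − 10 × 1)² / (16 × 16 × 7 × 25) = 4.57, p = 0.033. Power rises to 53.9% (d = 1.0) and 67.8% (d = 1.2), only 5 and 6 points below Wilcoxon. Its actual type I error is then the 0.083 from Step 1 (simulations gave 7.9% to 8.8%), not 5%.

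**Step 5. The p-value floor against the panel size.** Bonferroni across 797 genes requires p ≤ 0.05/797 = 0.000063. The Fisher floors in Step 1 all lie above this. Wilcoxon's floor at 7 successes is 2/3,365,856 = 0.0000006. Under Benjamini-Hochberg at 5%, genes at 0.0068 pass only if at least 0.0068 × 797/0.05 ≈ 108.4, so 109, of them reach that floor together.

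**The case against.** The strongest reply is that the sentence never says what one is tempted to read into it. A reader might infer that every gene will be cut in two at the median and scored yes or no. The documents do not say so. Status is undefined and could have more than two levels. The background uses similar words for markers that really are categorical, such as FGFR3 mutational status and positive Ang-2 expression by IHC (Section 1.1.2). The sentence might be meant only for IHC positivity, with the expression analysis left unspecified. That stands, and it limits the wording. It does not remove the gap: on either reading, quantitative expression has no suitable stated method.

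A second reply is that the power loss is not a property of the plan. It depends on the effect size, the cut, the number of successes and which of the two named tests is used. That also stands. The loss is not even monotone in the number of successes: at 8 of 32 it falls to about 19 points (d = 1.0), because Fisher's attainable size jumps about. At 35 patients the result depends on which side the median patient is put. With chi-square at 7 successes the power loss is small, though the type I error then exceeds 5%.

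A third is that calling most of the information lost would be too strong. Under the normal model the asymptotic relative efficiency of a median split is 2/3 against Wilcoxon, a loss of about one third. That is correct.

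Finally, moving about 800 genes to a 5% Wilcoxon test without a multiplicity rule would raise the expected false positives when no gene is associated, from about 797 × 0.0068 ≈ 5 to at most 797 × 0.05 ≈ 40. This is a fair criticism of a test swap on its own, and the fix has to meet it.

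**Conclusion.** The point holds as a minor one. The plan names only categorical tests for an undefined status, its main marker platform produces quantitative counts, and no cut-point or full-scale method is given. Under a median split, normal log-expression, a two-sided 5% level, a 1.0 to 1.2 SD shift and 5 to 7 successes among 32, Fisher's test gives up roughly 14 to 49 points of power against Wilcoxon. At 1.2 SD about 15 points of that is the split, and the remainder, largest at 7 successes, is Fisher's conservatism. Another cut, effect size or success count would change these figures.

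Two further inferences should be resisted. The p-value floor does not mean that the screen could show nothing: it rules out a Bonferroni pass, and under a false-discovery rule it requires many genes to reach the floor together. Nor does Wilcoxon make the screen well powered; it makes a strict threshold attainable, which is not the same as likely to be met with so few successes. No primary, secondary or safety conclusion is affected, because the work is exploratory, optional and conditional.

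**What to change.** In Section 8.3 and the synopsis, replace the biomarker sentence with text to this effect:

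- Normalised log2 Nanostring expression, and IHC scores recorded on an ordered scale, will be compared between PFS6 groups (and response groups) on their full scale by the exact Wilcoxon rank-sum test.
- Across the gene panel, a stated multiplicity rule will apply, for example the Benjamini-Hochberg false discovery rate at a named level, and all results will be labelled exploratory.
- Chi-square or Fisher's exact test will be used only for inherently categorical markers, such as histologic subtype. If an IHC status is wanted, its scoring and cut-point will be fixed before outcomes are examined.
- Any high/low grouping of a quantitative marker will be for display only.

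The cost is a few sentences in two places, with no extra patients, tissue or assays. The downside is that results are reported as a shift in expression or an AUC rather than as a high/low table.
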